6.5.4.1.2 Adverse event reporting period

The AE/SAE reporting period will be as follows:

Screening period: Any SAEs occurring between signing of the ICF and the first IMP dose should be reported to Sobi. For screen failures, any SAEs should be reported up to 28 days after ICF signature.

Treatment, maintenance and follow-up period: All AEs (including SAEs) occurring upon receiving the first IMP dose up to 8 weeks after last IMP administration must be recorded in the AE pages of the eCRF. In addition, SAEs should be reported to Sobi (see Section 6.5.4.1.4).

After follow-up period: After the 8-week AE follow-up period, new SAEs should be reported to Sobi only if considered causally related to previous exposure to the IMP by the investigator. These SAEs are only entered in the drug safety database and, hence, will not affect study closure.

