6.1 Overall study design and plan

This is a phase 3, randomized, double-blind, placebo-controlled multicenter study of pegcetacoplan (1080 mg) or placebo, administered twice weekly by s.c. infusion in patients with CAD.

A total of 57 patients with CAD will be enrolled in this study. Patients will be randomized in a ratio of 2:1 to receive either pegcetacoplan or placebo, respectively. The randomization will be stratified by transfusion history (number of transfusions during the 6-month period prior to randomization ≥ 1 ; 0). Every effort should be made to enroll patients in both subgroups.

The planned length of participation in the study for each patient is a maximum of 110 weeks. This study will consist of 5 periods:

- Screening period: up to 4 weeks (may be extended by up to 2 additional weeks).
- Double-blind treatment period: 24 weeks (Part A).
- Open-label treatment period: 24 weeks (Part B).
- Open-label maintenance period: up to additional 48 weeks or until the product becomes commercially available (Part C).
- Follow-up period: 8 weeks.

The study design is outlined in Figure 1, and the visit schedule and planned assessments at each visit are detailed in Table 1 and Table 2.

No formal interim analyses are planned. However, data will be reported for Part A (double-blind treatment period) once all patients have completed their Week 24 visit (or have early discontinued) and the database has been cleaned and verified for all visits up to and including Week 24. Similarly, data will be reported after Part B (see Section 8.3.7).

6.1.1 Screening period (up to 4 weeks; may be extended by up to 2 additional weeks)

Informed consent will be obtained during a screening visit prior to any study-related procedures being conducted. Patients experiencing acute hemolytic crisis may receive blood cell transfusions during the screening period. The start of dosing must occur at least 7 days after receiving last transfusion.

Patients will be screened to confirm that entrance criteria for the study have been met. Key inclusion and exclusion criteria will be reviewed by the study medical monitor and eligibility

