6.4.1.2 Vaccination and preventive antibiotics

6.4.1.2.1 Vaccination

To receive treatment with IMP, patients will be required to be vaccinated as per ACIP recommendations for adults or children with complement deficiencies and/or immunocompromising conditions (available at <https://www.cdc.gov/vaccines/schedules/hcp/index.html>) as follows:

Patients previously vaccinated will have documented evidence of vaccination against the following within 2 years of screening: *N. meningitidis* Types A, C, W, Y, and B (administered as 2 separate vaccinations), *S. pneumoniae* (with a PCV13 or PPSV23 vaccine), and *H. influenzae* Type B (Hib) vaccine (see Section 6.3.1, Inclusion Criterion #7).

Patients not previously vaccinated will have to receive vaccines during screening as follows:

- First dose of vaccine against *N. meningitidis* Types A, C, W, and Y at least 2 weeks prior to start of study drug with second dose 2 months later (study Day 57), and then boosters every 5 years.
- First dose of the vaccine against *N. meningitidis* Type B at least 2 weeks prior to start of study drug with a second dose after at least 1 month (study Day 29). First booster dose 1 year later, and then additional booster doses every 2 to 3 years.
- *S. pneumoniae*: PCV13 and/or PPSV23 as per ACIP guidelines for adults or children with immunocompromising conditions.
- *H. influenzae* Type B: 1 dose at least 2 weeks prior to start of study drug.

Vaccination is mandatory, unless documented evidence exists that patients are nonresponders to vaccination. Documented evidence that a patient is a nonresponder to vaccination should be provided via serological result (after second dose or booster where applicable). The investigator will discuss with the sponsor regarding individual patient circumstances.

Vaccines will be sourced locally by the study sites and reimbursed by the sponsor, or sourced by the sponsor if local sourcing is not feasible.

An AxMP is a medicinal product used for the needs of a clinical study as described in the protocol, but not as an IMP. In this study, the described mandatory vaccines are considered as AxMP and safety reporting applies for them, see Sections 6.5.4.1.3.1 and 6.5.4.1.4.1.

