For any AE, a diagnosis should be recorded rather than individual signs and symptoms or abnormal laboratory findings. However, if at the time of AE reporting a diagnosis is not available, each individual sign/symptom should be recorded. If a diagnosis is subsequently established, all previously reported AEs based on signs and symptoms should be removed and replaced by one AE report based on the single diagnosis, with a starting date that corresponds to the start date of the first symptom of the eventual diagnosis. This approach also applies to signs and symptoms of CAD worsening, which should be reported as “CAD worsening/progression” or similar (e.g., relapse, flare progression or exacerbation), as appropriate.

Procedures

Diagnostic and therapeutic noninvasive and invasive procedures, such as surgery, should not be reported as AEs. However, the medical condition for which the procedure was performed should be reported if it meets the definition of an AE. For example, an acute appendicitis that begins during the AE reporting period should be reported as the AE and the resulting appendectomy entered in the comments section of the eCRF.

Treatment-emergent adverse event

A treatment-emergent AE is any AE temporally associated with the use of study treatment, i.e., from study treatment initiation until 8 weeks after study treatment discontinuation.

Serious adverse event

An AE that meets one or more of the following criteria/outcomes is classified as serious:

- Results in death.
- Is life threatening (i.e., at immediate risk of death).
- Requires in-patient hospitalization or prolongation of existing hospitalization.
- Results in persistent or significant disability/incapacity.
- Is a congenital anomaly/birth defect (i.e., in an offspring to the study patient).
- Is a medically important AE.

Medically important AEs are events that may not result in death, be life threatening, or require hospitalization but may be considered serious when, based upon appropriate medical judgment, may jeopardize the patient or subject or may require medical or surgical intervention to prevent one of the outcomes listed above. Examples of such events are intensive treatment in an emergency room or at home for allergic bronchospasm, blood dyscrasias or convulsions that do not result in hospitalization or development of dependency or abuse.

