Serious also includes any other event that the investigator or company judges to be serious. Any suspected transmission of an infectious agent via IMP shall also be considered serious.

Hospitalization

In general, hospitalization means that the patient has been detained (usually involving at least an overnight stay) at the hospital or emergency ward for observation and/or treatment that would not have been appropriate in the physician's office or outpatient setting. When in doubt as to whether hospitalization occurred or was necessary, the AE should be considered serious.

The following situations are not considered hospitalizations (although other SAE criteria may still apply):

- Outpatient procedures/ambulatory care.
- Emergency department visits.

Hospitalization in the absence of an AE occurring during the study should not be considered an SAE. This includes:

- Pre-planned hospitalization due to a preexisting condition not associated with a worsening of the preexisting condition.
- Protocol specified admission.
- Elective admission, e.g., due to cosmetic surgery.
- Social admittance (e.g., stay overnight due to travel reasons).

Complications that occur during hospitalization should not be considered SAEs unless the complication prolongs hospitalization.

Suspected unexpected serious adverse reaction

A SUSAR is an untoward and unintended response to a study drug that is not listed in the reference safety information of the IB, meets at least 1 of the seriousness criteria, and is assessed as causally related to the IMP.

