6.5.4.1.3 Obtaining and recording adverse event information

The investigator obtains AE information that is directly observed or solicited from the patient or patient relative during the course of the study. All AEs must be recorded in the eCRF using concise medical terminology.

The investigator is responsible for obtaining sufficient information to determine seriousness, causality and outcome of each AE.

Severity assessment

The investigator will use the adjectives MILD, MODERATE, or SEVERE to describe the maximum severity of the AE. For the purpose of consistency, these severity grades are defined as follows:

MILD	Does not interfere with patient's usual function
MODERATE	Interferes to some extent with patient's usual function
SEVERE	Interferes significantly with patient's usual function

Note the distinction between the gravity (seriousness) and the severity of an AE. **Severe** is a measure of intensity; thus, a **severe** event is not necessarily a **serious** event. For example, a headache may be severe in intensity, but would not be classified as serious unless it met one of the criteria for serious events listed above.

Causality assessment

For each AE, the investigator must make a causality assessment to determine if there is a reasonable possibility that the IMP(s) caused the AE. The AE is assessed as **related** or **not related** to the IMP(s).

6.5.4.1.3.1 Reporting of adverse event to an auxiliary medicinal product

All AEs occurring after initiation of AxMP should also be reported in line with the reporting requirements stated above. Relationship to AxMP should be stated.

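### The SAE definition excludes in-hospital complications without keeping the other seriousness criteria; a lesser mismatch is a 28-day screen-failure SAE limit shorter than an extended screening

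*Protocol*

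**What the plan says.** **Seriousness.** Protocol 6.5.4.1.1 (Definitions) sets the general rule: "An AE that meets one or more of the following criteria/outcomes is classified as serious". Death and threat to life are separate entries in the list that follows, independent of the entry for hospitalization or a prolonged stay. Under the Hospitalization subheading the section adds: "Complications that occur during hospitalization should not be considered SAEs unless the complication prolongs hospitalization". A reminder that other criteria may still apply does appear under that subheading, but it introduces a different list, the one for outpatient procedures and emergency department visits.

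**Screening window.** Protocol 6.5.4.1.2 opens with a rule that has no day limit: "Any SAEs occurring between signing of the ICF and the first IMP dose should be reported to Sobi". The next sentence sets one: "For screen failures, any SAEs should be reported up to 28 days after ICF signature". Section 6.1 gives the length of screening: "Screening period: up to 4 weeks (may be extended by up to 2 additional weeks". The clock starts at the screening visit: "Informed consent will be obtained during a screening visit prior to any study-related procedures being conducted".

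**Vaccines.** Patients without current vaccination are vaccinated during screening. Section 6.4.1.2.1 states that "the described mandatory vaccines are considered as AxMP and safety reporting applies for them", and section 6.5.4.1.3.1 adds: "All AEs occurring after initiation of AxMP should also be reported in line with the reporting requirements stated above". In Table 1 the SAE row is marked for screening and the AE row is blank there. Table 5 has the same pattern.

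**The concern.** Seriousness decides how fast and by what route an event is handled. An SAE goes to the sponsor's safety group within 24 hours (6.5.4.1.4), and only a serious event can be a SUSAR. A non-serious event is entered in the eCRF, where section 9.2 only recommends entry within 5 working days. A site that applies the complication sentence as written could send a fatal or life-threatening in-hospital event down the slower route. Infection with encapsulated organisms is a potential risk named in section 4.3, so sepsis during an admission is a realistic example.

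The screening limit raises a smaller question. Study-required vaccines, and a bone marrow biopsy where none was done in the previous year, fall in a period that can outlast the 28 days. For a patient who fails late, the two sentences of 6.5.4.1.2 do not clearly agree on what must be reported.

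**Working it through.** **1. Maximum screening length.** Section 6.1 states a maximum participation of 110 weeks. The periods are screening, Part A (24 weeks), Part B (24), Part C (48) and follow-up (8).

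- With 6-week screening: 6 + 24 + 24 + 48 + 8 = 110 weeks, which reproduces the protocol's figure.
- With 4-week screening: 4 + 24 + 24 + 48 + 8 = 108 weeks.

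The protocol's own total therefore uses the extended screening, 6 × 7 = 42 days.

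**2. Gap against the screen-failure limit.** 42 − 28 = 14 days, that is days 29 to 42 after consent, or 14/42 = 33% of the longest possible screening. With unextended screening the gap is 28 − 28 = 0.

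**3. Who falls in the gap.** For an SAE on days 29 to 42:

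- Patient still in screening who is later dosed: reportable under the first sentence of 6.5.4.1.2. No gap.
- Patient still in screening who later fails: reportable under the first sentence when it occurs, but beyond the limit once the patient is classed as a screen failure. Ambiguous.
- Patient who has already failed: outside the limit.

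**4. Extreme case for vaccines.** First meningococcal and *H. influenzae* doses are due at least 14 days before study drug. With dosing on day 42, the latest such day is 42 − 14 = day 28 after consent, which leaves 28 − 28 = 0 days before the limit. With 4-week screening the latest day is 28 − 14 = day 14, which leaves 14 days. The zero describes the screen-failure sentence alone. While the patient remains in screening, the first sentence still applies.

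**5. Seriousness, side by side.** Take a complication that arises in hospital, is fatal or life threatening, and does not lengthen the stay.

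- General rule: one criterion is met, so the event is serious.
- Complication sentence: the stay is not prolonged, so the event is not an SAE.

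Both sentences are in 6.5.4.1.1 and neither yields to the other in the text. No arithmetic applies here.

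**The case against.** **On seriousness.** The sentence sits under the Hospitalization subheading and was probably meant to interpret that one criterion. The general rule is stated first, and 6.5.4.1.1 lets the investigator or the company judge any event serious. A reader might infer that the protocol deliberately makes fatal complications non-serious, or that such an event would disappear from the results. The documents support neither inference. SAP 7.6.1 tabulates treatment-emergent events leading to death and all events in the infections class, whatever their seriousness. What remains is that the judgement clause is discretionary, the reminder about other criteria is attached to another list, and the tables come long after the 24-hour deadline.

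**On the screening window.** The two sentences can be read together: the first covers everyone until dosing, and the second adds follow-up for those who fail early. The SAE mark in Table 1 covers the whole screening column, including the extension to Day -42. A reader might infer that a third of screening goes unmonitored, or that vaccinated patients have no SAE reporting at all. That is wrong while screening continues. The figures apply only to SAEs after day 28 in patients who have failed or later fail an extended screening. Screen failures who are never dosed are also outside the safety set, so no table of treated patients changes.

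**On the vaccine clause.** It can fairly be read as starting AE reporting at the first vaccine, with the reference to earlier requirements meaning only the manner of reporting. Protocol 8.3.5 and SAP 7.6.1 both plan a pretreatment AE summary, which fits that reading. It is therefore not established that non-serious vaccine reactions are lost. The blank screening cell and the start of AE recording at first IMP dose in 6.5.4.1.2 still point the other way.

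**Conclusion.** The contradiction on in-hospital complications stands and is the main point. Two sentences in one section classify the same event in opposite ways, and the consequence is possible loss of expedited reporting and SUSAR assessment, and absence from the SAE tables. This assumes a site follows the sentence literally. How often that happened cannot be judged from the documents.

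The screen-failure limit is a minor inconsistency: at most 14 days, only when screening was extended, and only for patients who failed. SAP 1.1 dates the end of enrollment at 10 January 2024, so it now matters only for the completeness of records already collected. The vaccine clause and the AE row are unclear, not demonstrably wrong. None of this affects the efficacy analysis, alpha or power.

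**What to change.** 1. In 6.5.4.1.1, extend the complication sentence with *or meets any other seriousness criterion*. Before reporting, check in-hospital complications recorded as non-serious against the full list of criteria.
2. In 6.5.4.1.2, end screen-failure SAE reporting at the later of 28 days after consent and confirmation of screen failure. With enrollment closed, the practical step is to check late failures from extended screenings for unreported SAEs. This wording does not cover events after a late failure is confirmed. A further period tied to the last study vaccine or biopsy would be the sponsor's choice, as the documents give no length for it.
3. State whether AE recording for the vaccines starts at the first vaccine dose, and make 6.5.4.1.2, 6.5.4.1.3.1 and the screening cell of the AE row in Tables 1 and 5 agree. Describe the pretreatment AE table in the same terms.

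The cost is a clause, a few sentences and one cell in each of two tables, plus a limited record check. It may add a few AE or SAE records.

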6.5.4.1.3 Obtaining and recording adverse event information

The investigator obtains AE information that is directly observed or solicited from the patient or patient relative during the course of the study. All AEs must be recorded in the eCRF using concise medical terminology.

The investigator is responsible for obtaining sufficient information to determine seriousness, causality and outcome of each AE.

Severity assessment

The investigator will use the adjectives MILD, MODERATE, or SEVERE to describe the maximum severity of the AE. For the purpose of consistency, these severity grades are defined as follows:

MILD	Does not interfere with patient's usual function
MODERATE	Interferes to some extent with patient's usual function
SEVERE	Interferes significantly with patient's usual function

Note the distinction between the gravity (seriousness) and the severity of an AE. **Severe** is a measure of intensity; thus, a **severe** event is not necessarily a **serious** event. For example, a headache may be severe in intensity, but would not be classified as serious unless it met one of the criteria for serious events listed above.

Causality assessment

For each AE, the investigator must make a causality assessment to determine if there is a reasonable possibility that the IMP(s) caused the AE. The AE is assessed as **related** or **not related** to the IMP(s).

6.5.4.1.3.1 Reporting of adverse event to an auxiliary medicinal product

All AEs occurring after initiation of AxMP should also be reported in line with the reporting requirements stated above. Relationship to AxMP should be stated.

6.5.4.1.4 Serious adverse event reporting

Both serious and nonserious AEs are to be reported on the AE page of the eCRF as specified in the eCRF instructions.

In addition, all SAEs must be reported by the investigator to the Sobi Global Pharmacovigilance & Patient Safety within 24 hours of the investigator's first knowledge of the event.

If an SAE occurs, it is to be notified by e-mail (e-mail address is indicated on the SAE form) using the designated Serious Adverse Event form.

The SAE collection form is not always the same as the AE eCRF form. The forms must be completed in a consistent manner. For example, the same AE term should be used on both forms.

All new information obtained, relevant to an SAE report, should be forwarded to Sobi Global Pharmacovigilance & Patient Safety within the same timeframe as the initial information.

If the patient is hospitalized in a hospital other than the study site, it is the investigator's responsibility to contact this hospital to obtain all SAE-relevant information and documentation.

New SAEs occurring after the 8-week AE follow-up period must be reported to Sobi Global Pharmacovigilance & Patient Safety within 24 hours of the investigator's knowledge of the event, only if considered causally related to previous exposure to the study treatment by the investigator.

The investigator shall provide Sobi Global Pharmacovigilance & Patient Safety with sufficient information to enable a complete medical assessment of the reported event. Best efforts shall be made by the investigator to provide Sobi Global Pharmacovigilance & Patient Safety with additional information related to any SAE as requested.

The reference safety document to assess expectedness of a suspect serious adverse reaction and reported by the sponsor to Health Authorities, IRBs/IECs, and investigators is the reference safety information section of the IB.

6.5.4.1.4.1 Reporting of serious adverse event to an auxiliary medicinal product

All SAEs occurring after initiation of AxMP should also be reported in line with the reporting requirements stated above. Relationship to AxMP should be stated.

6.5.4.1.5 Exposure during pregnancy and breastfeeding

If a woman becomes pregnant while on study treatment, study treatment must be discontinued. The investigator must counsel the patient and discuss the risks of continuing with the pregnancy and the possible effects on the fetus.

Any pregnancy occurring after study initiation (i.e., signing of ICF) up to 90 days following study treatment discontinuation must be reported within 24 hours of the investigator's knowledge of the event. This includes all situations where a woman is or has been found to be pregnant after being exposed to IMP – directly, indirectly or via her partner (paternal exposure).

All events of exposure to the IMP during pregnancy (female patient or male patient's partner) or breastfeeding, whether the exposure is associated with an AE or not, shall be reported to Sobi Global Pharmacovigilance & Patient Safety by e-mail using pregnancy notification form by e-mail (e-mail address is indicated on the pregnancy notification form).

In all reported situations of exposure during pregnancy, Sobi will provide the investigator with a Pregnancy report form that shall be completed and returned by the investigator. The investigator is responsible for monitoring the outcome of the pregnancy and to inform Sobi Global Pharmacovigilance & Patient Safety of relevant information and any information requested related to the outcome of the pregnancy.

Any AEs and SAEs observed during and in relation to pregnancy, delivery or breastfeeding should be recorded in the eCRF and, as applicable, be reported to Sobi Global Pharmacovigilance & Patient Safety as described previously in this section.

